4.4 COVARIATES

Table 4. Baseline Variables

Variable	Role	Operational definition
Age	Baseline characteristic and potential confounder	Age at index date
Sex	Baseline characteristic and potential confounder	
 1. Male 2. Female
Types of health insurance	Baseline characteristic and potential confounder	
Types of health insurance divided as the following:
 
 1. National Health Insurance 2. Medical aid

NIS Protocol <X9001134>
 Statistical Analysis Plan
 <Version 3.0> <03 May 2018>

Variable	Role	Operational definition
CHA ₂ DS ₂ -VASC	Baseline characteristic and potential confounder	
CHA₂DS₂-VASC as continuous data or dichotomous data. The score will be calculated using the following KCD codes (Appendix 2, Table 9):
 
 1. Congestive heart failure 2. Hypertension 3. Diabetes mellitus 4. Stroke/TIA/TE 5. Vascular disease 6. Age ≥ 75 7. Age 65-74 8. Female
HAS-BLED	Baseline characteristic and potential confounder	
HAS-BLED as continuous data or dichotomous data. The score will be calculated using the following KCD codes (Appendix 2, Table 10):
 
 1. Hypertension 2. Abnormal renal function 3. Abnormal liver function 4. Stroke 5. Bleeding history or predisposition: refers to any bleeding codes 6. Age > 65 7. Antiplatelet or NSAID use 8. Alcoholism 
[Note] Labile international normalized ratio is not available in HIRA data and does not apply to patients on aspirin, or NOACs, so the modified HAS-BLED score has a maximum value of 8 instead of 9.

Charlson Comorbidity Index	Baseline characteristic and potential confounder	Charlson Comorbidity Index as continuous data or dichotomous data. The index will be calculated using the following KCD codes (Appendix 2, Table 11):

NIS Protocol <X9001134>
Statistical Analysis Plan
<Version 3.0> <03 May 2018>

Variable	Role	Operational definition
		
1. Myocardial infarction2. Congestive heart failure3. Peripheral vascular disease4. Cerebrovascular disease5. Dementia6. Chronic pulmonary disease7. Rheumatic disease8. Peptic ulcer disease9. Mild liver disease10. Diabetes without chronic complication11. Diabetes with chronic complication12. Hemiplegia or paraplegia13. Renal disease14. Any malignancy, including lymphoma and leukemia, except malignant neoplasm of skin15. Moderate or severe liver disease16. Metastatic solid tumor17. AIDS/HIV
Baseline Medication Use	Baseline characteristic and potential confounder	
It will be consisted of the following (Appendix 2, Table 12):
 
1. NSAIDs2. Antiplatelet3. PPI4. H₂-receptor antagonists5. Antiarrhythmics6. Digoxin

Variable	Role	Operational definition
		7. Statins

4.5 HANDLING OF MISSING VALUES

After examining the characteristics of missing values, we will determine whether we can remove observations with missing values from the dataset. Basically, subjects with missing values of covariates will not contribute to the analysis.

5 STATISTICAL METHODOLOGY AND STATISTICAL ANALYSES

5.1 STATISTICAL METHODS

Descriptive Analysis:

- All outcome variables will be summarized descriptively through the tabular and graphical display of mean values, medians, ranges, and standard deviations for continuous variables of interest and frequency distributions for categorical variables.
- The proportion of antithrombotics (aspirin, clopidogrel, aspirin and clopidogrel combination, warfarin, NOACs) at index date will be examined.
- Appropriate tests (e.g., t-test, chi-square test) will be used based on the distribution of the measure. The $p < 0.05$ considered significant.

Multivariate Analysis:

Propensity score method

The estimation of propensity score will be performed to control for confounders in each sub-dataset: (1) each NOAC versus NOAC; (2) each NOAC versus warfarin; (3) each NOAC versus aspirin.

Propensity scores are estimated by logistic regression analyses that incorporate potential treatment predictors as independent variables and types of index treatment as dependent variable (e.g., apixaban=1, warfarin=0). Covariates in the logistic regression model will

include variables such as age, sex, CCI score, CHA₂DS₂-VASc score, HAS-BLED score, and comorbidities, but the final list of these covariates will be discussed and determined after reviewing the results of descriptive analysis of the pre-matched datasets. Further, we will report the *c*-statistic of the propensity score that indicates the degree to which the propensity score model discriminates between treated patients and untreated patients.

After estimation of propensity score, we will perform propensity score matching (PSM). 1:1 matching without replacement will be performed.

The populations would be first matched using PSM according to their index treatment. For these matched populations we should then explore the proposed subgroups by: making an assessment of patient numbers in the subgroups and checking that patient characteristics are still similar between the index treatments in the subgroups. If they are similar, then conduct interaction term analysis is being conducted to determine whether the treatment effect varies between the subgroups. If the populations are no longer similar in characteristics, then re-matching via PSM will be performed for the subgroups.

Covariate adjustment using propensity score will also be performed. This approach has an advantage of using the whole observations whereas matching approach uses part of observations which were successfully matched.

Inverse probability of treatment weighted (IPTW)

We will perform an inverse probability of treatment weighted (IPTW) analysis. Every person will be weighted by the inverse of the probability of receiving the treatment actually received (i.e., PS in the treated and (1-PS) in the untreated).

Balance diagnostics

We will compare and assess the balance of baseline variables (e.g., continuous variable, dichotomous variable, interaction terms, or squares of continuous variable) between treated and control subjects in the weighted sample using standardized difference (Austin et al., 2015).

IPTW diagnostics

The distribution of weights will be carefully checked because some patients, those treated contrary to prediction, may receive very large weights (11, 12). To address the presence of extreme weights, we will consider several approaches, including use of stabilized weights, or trimmed or truncated weights (11-13). The stabilized weights will be implemented based on the following equation (11):

IPTW stabilized = $E*PE/PS + (1-E)*(1-PE)/(1-PS)$

- E: treatment (E=1), no treatment (E=0).
- PE: overall marginal prevalence of the treatment exposure.
- PS: estimated propensity score.

Balances between treatment groups will be evaluated by the standardized differences of all covariates, using a threshold of 0.1 to determine an imbalance.

Cox proportional hazards model

Cox proportional hazards model will be used to compare event rates between the treatment groups, with warfarin or antiplatelets as the primary reference in each sub-dataset: (1) each NOAC versus NOAC; (2) each NOAC versus warfarin; (3) each NOAC versus aspirin.

Cox model stratification (dummy variable method and true stratification method) will be performed to examine whether the stratum-to-stratum differences exist. To check the proportional hazards assumption, we will employ both the graphical methods (i.e., log-log plot, observed-expected plot, Schoenfeld residual plot) and statistical tests using the time-dependent covariate. If the assumption does not meet, we will employ either a stratified model or an interaction term between time and variable of interest (i.e., treatment indicator).

The variables included in the model will be finalized after attempting model building process. Potential interactions will also be considered.

The hazard ratio and 95% confidence interval will be provided.

Sensitivity Analysis

Sensitivity analysis of performing IPTW using the propensity score derived from multinomial model will be conducted.

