## 8.7 Data analysis

- All outcome variables will be summarized descriptively through the tabular and graphical display of mean values, medians, ranges, and standard deviations of continuous variables of interest and frequency distributions for categorical variables.
- Patients with aspirin, warfarin, and NOACs will be matched via propensity-score method. Patients will be matched on patient demographics (i.e., age, sex) and clinical (i.e., CHA2DS2-VAsC score, Charlson Comorbidity Index score, etc) variables. Other propensity score method (i.e., covariate adjustment, inverse probability of treatment weighting (IPTW)) will also be used. A Cox proportional hazards model, to account for differences in follow-up time and right data censoring, will be used to compare effectiveness and safety outcomes between treatment groups.
- Comparative analyses will be performed contingent on a feasibility assessment based on the descriptive analyses
- All analyses will be carried out using SAS version 9.4. The 95% confidence intervals for the estimates will be calculated and p < 0.05 considered significant.
- Sensitivity analysis of performing IPTW using the propensity score derived from multinomial model will be conducted.

Detailed methodology for summary and statistical analyses of data collected in this study will be documented in a Statistical Analysis Plan (SAP), which will be dated, filed and maintained by the sponsor. The SAP may modify the plans outlined in the protocol; any major modifications of primary endpoint definitions or their analyses would be reflected in a protocol amendment.

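### The SAP names no variance estimator for its inverse-probability-weighted Cox models; with the ordinary model-based variance, their confidence intervals would be too narrow

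*SAP*

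**What the plan says.** SAP 5.1 sets out IPTW for the pairwise comparisons: "Every person will be weighted by the inverse of the probability of receiving the treatment actually received". The weight is therefore 1/PS in the treated and 1/(1-PS) in the untreated. Under the IPTW diagnostics the SAP adds: "To address the presence of extreme weights, we will consider several approaches, including use of stabilized weights, or trimmed or truncated weights". The next sentence begins "The stabilized weights will be implemented based on the following equation" and gives a two-group formula.

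The outcome model follows: "Cox proportional hazards model will be used to compare event rates between the treatment groups", and then "The hazard ratio and 95% confidence interval will be provided". Under the sensitivity analysis heading: "Sensitivity analysis of performing IPTW using the propensity score derived from multinomial model will be conducted". Protocol 8.7 adds: "The 95% confidence intervals for the estimates will be calculated and p < 0.05 considered significant". The example results table in SAP Appendix 1 has columns for the hazard ratio with its interval and for a p-value.

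IPTW is not the only method. SAP 5.1 also states "1:1 matching without replacement will be performed" and plans covariate adjustment on the propensity score. Protocol 8.7 and SAP 5.2 describe matching first and say that the other propensity-score methods will be used as well.

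Neither document mentions a robust, sandwich, bootstrap or model-based variance.

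**The concern.** The SAP specifies the propensity model, the weights, the weight diagnostics, the balance threshold and the proportional-hazards checks. It omits the step that makes a weighted interval valid.

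Unstabilised weights in a two-arm comparison sum to about twice the number of patients. The ordinary Cox variance treats that weighted total as real information, so the standard error is too small. This does not need extreme weights. If every patient had a propensity score of 0.5, every weight would equal 2, the diagnostics would show nothing unusual, and the standard error would still be wrong.

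At stake is the use of IPTW as a check on the matched result across up to nine pairwise sub-datasets, and the multinomial IPTW, which is the only analysis under the sensitivity heading. If those intervals are too narrow, the weighted analysis can seem to contradict or confirm the matched one purely by artefact. Two analysts who both follow the SAP could also report materially different intervals and p-values from the same data.

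**Working it through.** The documents give no power calculation, event count or expected error rate for the weighted models, so there is no figure to reproduce. The only anchor is the 0.05 level in Protocol 8.7, taken here as two-sided (critical value 1.96). Treatment shares, propensity-score spread and event rates are not given. All values below are assumptions, shown as a range.

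**Analytic check, two arms.** Let the propensity score be constant at p, with D events and no treatment effect.

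- True variance of the log hazard ratio: about 1/(Dp) + 1/(D(1-p)) = 1/(Dp(1-p)).
- Unstabilised weights turn the Dp treated events into D and the D(1-p) untreated events into D. The weighted total is 2D, with half the weighted risk set in each arm.
- Model-based information: 2D x 1/4 = D/2, so model-based variance = 2/D.
- Ratio of true to model-based variance: R = 1/(2p(1-p)), smallest at p = 0.5, where R = 2.
- False-positive rate: 2 x (1 - Phi(1.96/sqrt(R))).

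| Treatment split | R | True SE / model-based SE | False-positive rate |
|---|---|---|---|
| 50:50 | 2.000 | 1.414 | 16.6% |
| 40:60 | 2.083 | 1.443 | 17.5% |
| 30:70 | 2.381 | 1.543 | 20.4% |
| 25:75 | 2.667 | 1.633 | 23.0% |
| 20:80 | 3.125 | 1.768 | 26.8% |
| 10:90 | 5.556 | 2.357 | 40.6% |

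At 50:50 the interval has 1/1.414 = 0.71 of its correct width. With a constant propensity score the SAP's stabilised weights all equal 1, and the rate returns to 5%.

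**Simulation with a varying, estimated propensity score.** Setup: true hazard ratio 1, n = 5,000, about 5% with an event, four covariates, logistic propensity model, 2,400 replicates per scenario. The Monte Carlo standard error near 5% is sqrt(0.05 x 0.95/2400) = 0.4 percentage points. Slope is the log-odds slope of treatment on the covariate score; prognosis is the log-hazard slope on the same score.

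| Share | Slope | Prognosis | Unstabilised, model-based | Stabilised, model-based | Robust (either weight) |
|---|---|---|---|---|---|
| 50% | 0 | 0.5 | 17.2% | 5.5% | 5.5% |
| 50% | 0.5 | 0.5 | 17.8% | 6.3% | 5.4% |
| 50% | 1.0 | 0.5 | 23.7% | 8.8% | 5.0% |
| 30% | 0.5 | 0.5 | 18.8% | 5.0% | 4.9% |
| 30% | 1.0 | 0.5 | 24.5% | 8.4% | 5.7% |
| 20% | 0.5 | 0.5 | 24.9% | 5.0% | 5.0% |
| 50% | 0.5 | 0 | 17.4% | 5.4% | 4.8% |
| 30% | 1.0 | 0 | 29.7% | 12.3% | 6.7% |

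Stabilised weights truncated at the 1st and 99th percentiles gave 5.2-9.4% with the model-based variance and 4.8-6.3% with the robust one. Most of the excess therefore comes from the doubled apparent sample size. A smaller part remains after stabilising when propensity scores are widely spread. The robust (Lin-Wei sandwich) variance removes nearly all of both.

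**The case against.** The strongest reply is that silence is not a plan. Nothing in either document calls for a model-based variance, and an analyst who used a sandwich variance would comply fully with the SAP. This stands. A reader might infer that the sponsor intends invalid intervals, or that 17-25% is the plan's actual error rate. The documents support neither. The harm depends on a choice they leave open.

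A second reply is that the SAP prints a stabilised formula, under which the inflation is much smaller. This stands in part. The sentence carrying the formula could be read as a commitment, but the sentence before it only considers stabilisation, alongside trimming and truncation, for extreme weights. The one weight stated without condition is the unstabilised one. The formula also covers two groups only, so it does not define a weight for the multinomial model.

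Third, IPTW is additional to matching. This stands: neither matching nor covariate adjustment uses weights, so nothing here shows their intervals to be wrong. It would also go too far to infer from this point that the matched analyses need a different variance; the calculations do not address that.

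Finally, a reader might extend the argument to one error rate for the multinomial model. The documents give neither its number of categories nor the treatment shares. With constant propensity scores and unstabilised weights, the variance ratio for arms j and k is (1/pj + 1/pk)/2. That is 10 for shares of 10% each and 2.9 for shares of 40% and 30%, so no single figure is defensible.

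**Conclusion.** The point holds as a conditional one. The SAP leaves open both the variance estimator and the default weight for its IPTW Cox models, and taking its stated weight into a standard Cox fit gives intervals that are too narrow.

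For two arms, the type I error under a model-based variance would be about 17-25% with unstabilised weights. This assumes treatment shares of about 25-50% and moderate propensity-score spread. It rises with more unequal shares (26.8% at 20:80 and 40.6% at 10:90 in the analytic check), and it reached 29.7% in one scenario with wide spread and non-prognostic covariates. With the stabilised formula it would be about 5-12%, and with a robust variance about 5-7%.

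The conclusion is limited to the pairwise IPTW analyses and the multinomial IPTW sensitivity analysis. For the latter, the direction of the problem is clear but its size cannot be given from the documents. This should be settled before the weighted analyses are run.

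**What to change.** Add to SAP 5.1, for all IPTW Cox models both pairwise and multinomial: stabilised weights are the default, and standard errors, confidence intervals and p-values come from a robust sandwich variance or from a bootstrap that re-estimates the propensity score in each resample. State the stabilised weight for the multinomial model as well, as the overall share of the treatment received divided by its estimated probability. Trimming or truncation can remain a response to extreme weights.

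The robust variance is the essential part. In the simulation it gave the same rates, to the precision shown, for both weight types. Stabilising by default removes the doubled sample size and limits the damage if the variance option is missed.

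The cost is one sentence and one program option. Intervals will be somewhat wider than under a model-based variance, and correct.

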5.2 STATISTICAL ANALYSES

- Patients with aspirin, warfarin, and NOACs will be matched via propensity-score method. Patients will be matched on patient demographics (i.e., age, sex) and clinical (i.e., CHA₂DS₂-VASc score, Charlson Comorbidity Index score, etc.) variables. Other propensity score method (i.e., covariate adjustment, IPTW) will

also be used. Standardized difference will be used to assess the balance of variables after matching. A standardized difference < 10% will be considered acceptable.

- A Cox proportional hazards model, to account for differences in follow-up time and right data censoring, will be used to compare effectiveness and safety outcomes between treatment groups.

6 SUMMARY OF ANALYSES

Outcome	Supports Protocol Objective Number	Statistical Method	Covariates/ Strata
Baseline characteristics and drug utilization patterns	1	Chi-square test, t-test	Demographic and clinical characteristics, including baseline comorbidities
Stroke/systemic embolism	2	Propensity score method, Cox proportional hazards model	Demographic and clinical characteristics, including baseline comorbidities
Major bleeding	3	Propensity score method, Cox proportional hazards model	Demographic and clinical characteristics, including baseline comorbidities

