2.2 STUDY OBJECTIVES

Primary objectives

1. To explore baseline characteristics and drug utilization patterns in patients with nonvalvular atrial fibrillation (NVAF) who newly initiated NOACs, warfarin, or used aspirin
 - Demographic and clinical characteristics: Age, sex, types of health insurance, CHA₂DS₂-VASc score, HAS-BLED score, Charlson Comorbidity Index score, etc.
 - Descriptions of index treatment: Types of medication received, index dose intensity
 - Drug utilization pattern: Each patient will be followed-up until the first treatment modification occurs, or study ends (November 30, 2016).
2. To compare effectiveness including hemorrhagic stroke, ischemic stroke and systemic embolism of antithrombotic therapies in patients with NVAF with the following antithrombotic therapies: NOACs, warfarin, and aspirin
 - Primary effectiveness outcome: Composite of hemorrhagic stroke, ischemic stroke, and systemic embolism
 - Secondary effectiveness outcomes: Individual outcome of hemorrhagic stroke, ischemic stroke, and systemic embolism
3. To compare safety of anti-thrombotic therapies in patients with NVAF with the following antithrombotic therapies: NOACs, warfarin, and aspirin
 - Primary safety outcome: Major bleeding including gastrointestinal bleeding or intracranial bleeding and other bleeding
 - Secondary safety outcomes: Individual outcome of major bleeding

[NOTE] comparative analyses will be performed contingent on a feasibility assessment based on the descriptive analyses.

Secondary objectives

1. To explore and understand more detailed drug utilization patterns
 - Standard dose versus reduced dose

- Pattern of usage (i.e., switching, discontinuation) and clinical events preceding the pattern
- Compliance (i.e., medication possession ratio)

2. To compare effectiveness and safety of antithrombotic therapies versus not using therapies among low risk patients (low score of CHA₂DS₂-VASc)

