3 ANALYSIS SETS/ POPULATIONS

3.1 FULL ANALYSIS SET

Inclusion criteria

Patients must meet all of the following inclusion criteria to be eligible for inclusion in the study:

1. Patients aged 18 years or older on the index date
2. Patients had ≥ 1 medical claim for AF (refer to Table 1) before or on the index date with at least one hospitalization or at least two outpatient visits:

[Diagnosis codes for inclusion criteria]

KCD-6 ¹⁾	KCD-7 ²⁾
I48 (Atrial fibrillation and flutter)	I48 (Atrial fibrillation and flutter)
I480 (Atrial fibrillation)	I480 (Paroxysmal atrial fibrillation)
I481 (Atrial flutter)	I481 (Persistent atrial fibrillation)
	I482 (Chronic atrial fibrillation)
	I483 (Typical atrial flutter)
	I484 (Atypical atrial flutter)
	I489 (Atrial fibrillation and atrial flutter, unspecified)

KCD-6, Korean version of ICD-10 (6th revision); KCD-7, Korean version of ICD-10 (7th revision)

1) KCD-6 diagnosis codes will be used from 1 July 2015 to 31 December 2015.

2) KCD-7 diagnosis codes will be used from 1 January 2016 to 30 November 2016.

[NOTE] KCD code is based on ICD-10 and almost similar, but KCD code is slightly different from ICD-10 (e.g., ICD-10 is more subdivided and extensive than KCD code).

3. Patients prescribed aspirin, warfarin, or NOACs in intake period (from July 1, 2015 to November 30, 2016)
[Note] NOACs include apixaban, dabigatran and rivaroxaban.

Exclusion criteria

Patients meeting any of the following criteria will not be included in the study.

1. Medical claims indicating diagnosis or procedure for hip/knee replacement surgery within 6 weeks prior to index date
2. Medical claims indicating a diagnosis code indicative of rheumatic mitral valvular heart disease, mitral valve stenosis during the 12-month baseline period
(Valvular AF / Prosthetic heart valves)
3. Medical claims indicating a diagnosis code of VTE (Venous thromboembolism) during the 12-month baseline period
4. Medical claims indicating a diagnosis or procedure code of transient AF, or cardiac surgery during the 12-month baseline period
(Thyrotoxicosis, Hypertrophic cardiomyopathy, elective defibrillation, radiofrequency ablation, or left atrial appendage occlusion)
5. Medical claims indicating a diagnosis code of others during the 12-month baseline period
 - (End-stage chronic kidney disease / Kidney transplant / Dialysis / Pericarditis)

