4.3 OTHER ENDPOINTS

Table 3. Other Endpoints

Variable	Role	Operational definition
Discontinuation	Outcome	Discontinuation is defined as the first day of a period of at least 30 consecutive days after the calculated time to finishing the pack based on pack size and number of tablets per day. The date of discontinuation will be the end date of the last filled prescription before the treatment gap.
Switching	Outcome	A switch among anticoagulants will be defined as a prescription filled for non-index OAC within 30

Variable	Role	Operational definition
		days after the date of discontinuation.
Clinical events preceding each pattern	Outcome	
Types of event* preceding each pattern (i.e., discontinuation, switching)
 
[*Note] Events will include but not limited to (1) serious clinical events where physicians might consider changing anticoagulants (e.g., thromboembolic events (e.g., stroke/systemic embolism, venous thromboembolism [codes in Table 7]), major bleeding [codes in Table 8]); (2) the occurrence of a contraindication for OACs (e.g., valvular atrial fibrillation, severe kidney disease); and (3) procedure for atrial fibrillation that might not require OACs (e.g., elective defibrillation, radiofrequency ablation, and left atrial appendage occlusion [codes in Table 13]).

Compliance (medication possession ratio, MPR)	Outcome	
Medication possession ratio (MPR) will be calculated as total days of index treatment dispensed / 365 days of study follow-up.
 
Patients with an MPR greater than 1 will be capped at 1.

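### SAP 6 gives discontinuation and switching only chi-square and t-test, although possible observation runs from 0 to 518 days and no censoring is handled

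*SAP*

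**What the plan says.** SAP 2.2 places drug utilization under primary objective 1 and sets its observation period: "Each patient will be followed-up until the first treatment modification occurs, or study ends (November 30, 2016"). Intake closes on that same date. The third inclusion criterion in SAP 3.1 reads "Patients prescribed aspirin, warfarin, or NOACs in intake period (from July 1, 2015 to November 30, 2016"), and no minimum follow-up is required.

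SAP 4.3, Table 3, gives discontinuation and switching the role of outcomes. For the first: "Discontinuation is defined as the first day of a period of at least 30 consecutive days after the calculated time to finishing the pack". The event is dated at the end of the last filled prescription before the gap. For the second: "A switch among anticoagulants will be defined as a prescription filled for non-index OAC within 30" days after the date of discontinuation.

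For the row that combines baseline characteristics and drug utilization patterns, SAP 6 lists "Chi-square test, t-test" and nothing else. SAP 5.1, under descriptive analysis, says "Appropriate tests (e.g., t-test, chi-square test) will be used based on the distribution of the measure", with p < 0.05 taken as significant. The Cox model, which SAP 5.2 justifies by differing follow-up and right censoring, "will be used to compare effectiveness and safety outcomes between treatment groups". No Kaplan-Meier curve, cumulative incidence, person-time rate or fixed observation window is planned for discontinuation or switching. The 365-day denominator in Table 3 applies only to the medication possession ratio.

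**The concern.** The plan recognises unequal follow-up and censoring for stroke, embolism and bleeding. The same patients have the same administrative end date when the outcome is stopping or switching, yet there the plan names only tests that ignore time.

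Two things are at stake. First, a crude percentage discontinued mixes patients observed for 17 months with patients observed for days. It describes no stated period and is too low. Second, if one drug was started later than another on average, a crude comparison partly measures calendar time. A proportion and a mean number of days on treatment would then mislead in opposite directions. Utilization is one of the three primary objectives, so these figures will be reported and read.

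**Working it through.** The plan states no expected discontinuation figure, so there is nothing of its own to reproduce. The dates come from the SAP. The discontinuation rates, start-date patterns and group sizes below are assumptions, shown as ranges.

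**Observation range.** 1 July 2015 to 30 November 2016 is W = 518 days. A full 365 days is possible only for index dates up to 1 December 2015, which is (518 − 365)/518 = 29.5% of the window.

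**Confirmation limit.** 30 November minus 30 days is 31 October 2016. Later supply ends cannot meet the 30-day gap. The usable window is 518 − 30 = 488 days at most.

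**Level.** Assume an exponential time to discontinuation with 12-month risk p, so h = −ln(1 − p)/365. With uniform starts the crude proportion is

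[488 − (1 − e^(−488h))/h] / 518.

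For p = 40%: h = 0.0013995, e^(−488h) = 0.505, (1 − 0.505)/h = 353.6, and (488 − 353.6)/518 = 25.9%. The risk over the full 518 days is 1 − e^(−518h) = 51.6%, so the crude figure is low against either reference.

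**Dependence on start dates, with the same true hazard throughout.** The starts are uniform, linearly rising or linearly falling over intake:

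| Assumed 12-month risk | Uniform | Rising (late) | Falling (early) |
|---|---|---|---|
| 30% | 19.3% | 12.6% | 26.0% |
| 40% | 25.9% | 17.2% | 34.7% |
| 60% | 39.9% | 27.4% | 52.4% |

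Uniform against rising starts with 2,000 patients per drug, p = 40%: the pooled proportion is 0.2156 and z = 0.0877/√(0.2156 × 0.7844 × 2/2000) = 6.7. Across the three risks z runs from 5.8 to 8.4, with no true difference.

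**Direction of each test.** In a simulation (1,000 runs, 1,000 per arm, true 12-month risk 50% in both), one drug's starts were uniform over the first 398 days of intake and the other's over the last 398, so mean start differed by 120 days.

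- Crude proportion discontinued: 40.9% (earlier drug) against 25.9% (later drug). Chi-square rejected in 100% of runs.
- Mean observed days on treatment: 215 against 136. The t-test also rejected in 100% of runs, in the opposite direction.
- Log-rank with administrative censoring rejected in 4.5% of runs, close to the nominal 5%.
- With identical start distributions, chi-square, t-test and log-rank rejected in 4.8%, 4.2% and 4.7%.

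**A contrast suggested by the plan's own rules.** SAP 3.1 indexes aspirin users at their first prescription in intake and allows prior use, whereas NOAC users must be free of anticoagulants for a year. Existing aspirin users would tend to be indexed early. If aspirin starts fell in the first 90 days and NOAC starts were uniform, equal hazards would give crude figures of 35.1% against 19.3%, 46.2% against 25.9%, and 67.1% against 39.9% for p = 30%, 40% and 60%. At 500 per arm, z is 5.6 to 8.6. The 90-day clustering is an assumption.

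**The case against.** The SAP 6 row is a one-line summary, and much of what it covers (baseline characteristics, index drug, index dose) is uncensored and suits these tests. SAP 5.1 offers the tests as examples. The table shells show no persistence comparison. Objective 1 is worded as exploration, and discontinuation and switching are named expressly under a secondary objective. On this view the plan merely leaves their analysis unspecified.

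Part of this stands: no passage states outright that crude proportions discontinued will be tested between drugs, and no confirmatory claim rests on one. It does not remove the point. Primary objective 1 itself includes follow-up to the first treatment modification, SAP 6 lists the two tests without any hedge, and SAP 5.1 ties the choice of test to the distribution of the measure, not to censoring. Even as pure description, a crude percentage is the wrong summary.

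A reader might go further and infer that later-started drugs will look more persistent and that chi-square will almost always find a false difference. The documents do not support that. They give no start-date distribution by drug. With equal start dates chi-square keeps its error rate and only the level is wrong, and the t-test on days errs the other way.

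**Conclusion.** The point holds as a gap in the analysis of two utilization endpoints. Two parts follow from the plan's dates and definitions alone: observation from 0 to 518 days, and no confirmable discontinuation for supply ending after 31 October 2016.

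Crude percentages therefore understate, for every drug, the discontinuation that complete follow-up over the window would show. Under uniform starts and an exponential model, 25.9% is observed against an assumed 12-month 40% (19.3% against 30%, 39.9% against 60%). They are not tied to 12 months either: if all starts fell in the first 90 days, the crude figure would be 46.2% against that 40%.

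Bias between drugs is conditional on their start dates differing. The aspirin index rule makes a difference plausible, but its size is not documented, and the contrasts above illustrate it without predicting it. The effectiveness and safety comparisons are unaffected.

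**What to change.** In SAP 5.1 and SAP 6, split the combined row.

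1. Keep chi-square and t-test for baseline characteristics and index-date treatment only.
2. Analyse any discontinuation by Kaplan-Meier from the index date, with supply end as the event date and administrative censoring at 31 October 2016. Compare drugs by log-rank or Cox.
3. For the split by type, classify each discontinuation as one of two mutually exclusive events, both dated at supply end: switched (a non-index OAC filled within 30 days, as in Table 3) or stopped without a switch. Report cumulative incidence as competing events at fixed times, for example 3, 6 and 12 months, with Gray's test or cause-specific Cox.

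The reclassification in step 3 is needed. Under Table 3 a switch is dated from a discontinuation and is a subset of it, so the two endpoints as now defined cannot compete with each other.

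The cost is SAP wording, including the event classification, and a little more programming. No new data are needed. Supply ends in November 2016 are not used for these endpoints.
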